During the double-blind treatment period (between Visit 2 and Visit 4), participants will have up to 60 days to treat 2 qualifying prodrome events, as defined above, with study intervention. Participants should treat as soon as they are confident that a headache will inevitably follow their prodrome symptoms.

eDiary Assessments

During both the screening and double-blind treatment periods, the participant will report information in the eDiary at the time of each qualifying prodrome event:

- Confirmation that the participant is experiencing a qualifying prodrome event
- Identification and intensity of individually specific prodrome symptom(s)
- Headache pain and intensity (if it occurs)
- Nonheadache symptoms (photophobia, phonophobia, nausea, dizziness) including intensity (mild, moderate, severe)
- Presence or absence of aura
- Health Outcomes assessments

Participants will be asked to complete their eDiary at prespecified timepoints (1, 2, 3, 4, 6, 8, 24, and 48 hours) and on an event-driven basis (ie, when a headache occurs). In addition, in the double-blind treatment period, the date and time of when double-blind study intervention is taken will be captured, as well as rescue medication use.

Visit Schedule

In addition to the Screening Visit (Visit 1) and Randomization Visit (Visit 2) described above, participants will return to the clinic for the Posttreatment Visit (Visit 3) after the first qualifying prodrome event is treated, 4 days after taking double-blind study intervention. The first and second qualifying prodrome events must be 2 separate and distinct events that are at least 7 days apart. Participants unable to treat 2 qualifying prodrome events during the double-blind treatment period will be discontinued from the study.

Participants will return to the clinic for Visit 4 after the second qualifying prodrome event is treated, 4 days after taking double-blind study intervention. Visit 4 will be conducted for randomized participants who prematurely discontinue during the double-blind treatment period, regardless of whether or not they took study intervention. For additional information on study visits and procedures, please see the SoA (Section 1.3). The sequence of events during the screening and double-blind treatment periods are displayed below in Figure 4-2.

25

Figure 4-2 Screening Period

[figure not shown]
[figure not shown]

Figure 4-3 Double-blind Treatment Period

26

Efficacy, Safety, and Pharmacokinetic Assessments

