8.1. Efficacy Assessments

Efficacy measurement assessments are based on information recorded by the participant in an eDiary.

Absence/Presence of and Rating of Intensity of Prodrome Symptom(s)

After experiencing each qualifying prodrome event, the absence or presence of each identified prodrome symptom(s) will be followed (up to 48 hours) and the intensity subjectively rated (mild, moderate, or severe) for those that are present.

Absence/Presence of Headache and Rating of Headache Intensity

After the prodrome symptoms have started, the participant will be alerted to record the presence of a headache when it occurs or record the absence/presence at various timepoints (up to 48 hours) following the dose of double-blind study intervention (during the double-blind treatment period). If a headache is reported as present, the intensity will be subjectively rated (mild, moderate, or severe).

Absence/Presence of and Rating of Intensity of Nonheadache Symptoms

The participant will record whether nonheadache symptoms (photophobia, phonophobia, nausea, and/or dizziness) were absent or present as well as the intensity (mild, moderate, or severe) of the present nonheadache symptom (up to 48 hours).

50

Absence/Presence of Aura

The participant will record whether aura was present or absent (up to 48 hours).

Health outcomes assessments are described in Section 8.10.

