9.4.1.1. Analysis Endpoints

The primary and secondary efficacy endpoints are listed below and analyses will be defined in the following sections. All analyses for other efficacy endpoints listed below will be defined in the SAP.

Primary efficacy endpoint:

• Absence of a headache of moderate/severe intensity within 24 hours after taking double-blind study intervention during the prodrome

Secondary efficacy endpoints:

- Absence of a headache of moderate or severe intensity within 48 hours after taking double-blind study intervention during the prodrome
- Ability to function normally over 24 hours after taking double-blind study intervention during the prodrome
- Absence of a headache of any intensity within 24 hours after taking double-blind study intervention during the prodrome

Additional endpoints:

- Absence of headache of any intensity by timepoint (excluding the endpoints that are already captured as primary and secondary endpoints)
- Absence of moderate/severe headache by timepoint (excluding the endpoints that are already captured as primary and secondary endpoints)
- Absence of severe headache by timepoint
- Time to development of headache of any intensity within 48 hours after taking double-blind study intervention during the prodrome (Kaplan-Meier analysis)
- Time to development of headache of moderate/severe intensity within 48 hours after taking double-blind study intervention during the prodrome (Kaplan-Meier analysis)
- Time to development of headache of severe intensity within 48 hours after taking double-blind study intervention during the prodrome (Kaplan-Meier analysis)
- For each of the 5 most common individual prodrome symptoms:
 - o Absence of any intensity at each timepoint
 - o Absence of moderate/severe intensity at each timepoint
 - o Absence of severe intensity at each timepoint
 - o Time to absence of any intensity
- After a headache of any intensity is reported:
 - Absence of nonheadache migraine symptoms (photophobia, phonophobia, nausea, dizziness) at each timepoint
 - Absence of nonheadache migraine symptoms (photophobia, phonophobia, nausea, dizziness) of moderate/severe intensity at each timepoint
 - Absence of nonheadache migraine symptoms (photophobia, phonophobia, nausea, dizziness) of severe at each timepoint
- Absence of aura at each timepoint
- Rescue medication use within 24 and 48 hours after taking double-blind study intervention

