9.4.1.4. Other Efficacy Analyses

The absence of a headache of any intensity by each timepoint after taking double-blind study intervention will be analyzed using the same GLMM model as primary endpoint. Similar analyses will be performed for the absence of a headache of moderate/severe intensity and absence of severe headache by timepoint. Kaplan-Meier curves for time to development of any intensity headache (or rescue medication taken), time to development of moderate/severe headache, time to development of severe headache within 48 hours will be produced by treatment and compared between treatment using the log-rank test. Additional Kaplan-Meier curves will be generated treating rescue medication as an event for the time to development of moderate/severe intensity headache and time to development of severe headache.

For each of the 5 most common individual prodrome symptoms, the absence of any intensity, absence of moderate/severe intensity, absence of severe intensity at each timepoint will be analyzed using the same GLMM model as primary endpoint. Similar analyses will be performed for the absence of any intensity nonheadache migraine symptom, absence of moderate/severe nonheadache migraine symptom, absence of severe nonheadache migraine symptom at each timepoint, and absence of aura at each timepoint. Kaplan-Meier curves for time to absence of prodrome symptoms will be produced by treatment and compared between treatment using the log-rank test. Kaplan-Meier curves will also be generated censoring data collected after rescue medication.

The observed proportions of participants who used rescue medication within 24 and 48 hours after taking double-blind study intervention will be summarized and analyzed using the same GLMM model as primary endpoint. The treatment comparisons will be conducted using the primary model. Kaplan-Meier curves for time to rescue medication use within 48 hours after taking double-blind study intervention will also be produced by treatment and compared by log-rank test.

Analysis methods for the endpoints of satisfaction with study medication and Activity Limitation will be specified in the SAP.

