1.2 Migraine with aura

Previously used terms: Classic or classical migraine; ophthalmic, hemiparaesthetic, hemiplegic or aphasic migraine; migraine accompagnee; complicated migraine.

Description: Recurrent attacks, lasting minutes, of unilateral fully reversible visual, sensory or other central nervous system symptoms that usually develop gradually and are usually followed by headache and associated migraine symptoms.

Diagnostic criteria:

- A. At least two attacks fulfilling criteria B and C
- B. One or more of the following fully reversible aura symptoms:
 - 1. visual
 - 2. sensory
 - 3. speech and/or language
 - 4. motor
 - 5. brainstem
 - 6. retinal
- C. At least three of the following six characteristics:
 - 1. at least one aura symptom spreads gradually over ≥5 minutes
 - 2. two or more aura symptoms occur in succession
 - 3. each individual aura symptom lasts 5–60 minutes¹
 - 4. at least one aura symptom is unilateral²
 - 5. at least one aura symptom is positive³
 - 6. the aura is accompanied, or followed within 60 minutes, by headache
- D. Not better accounted for by another ICHD-3 diagnosis.

Notes:

- 1. When, for example, three symptoms occur during an aura, the acceptable maximal duration is 3 x 60 minutes. Motor symptoms may last up to 72 hours.
- 2. Aphasia is always regarded as a unilateral symptom; dysarthria may or may not be.
- 3. Scintillations and pins and needles are positive symptoms of aura.

Comments: Many patients who have migraine attacks with aura also have attacks without aura; they should be coded as both 1.2 Migraine with aura and 1.1 Migraine without aura.

Field testing has compared the diagnostic criteria for 1.2 *Migraine with aura* in the main body of ICHD-3 beta with those for A1.2 *Migraine with aura* in the Appendix. The latter performed better in distinguishing migraine with aura from transient ischaemic attacks. These are now adopted in ICHD-3, which no longer has Appendix criteria for this disorder.

The aura is the complex of neurological symptoms that occurs usually before the headache of 1.2 *Migraine with aura*, but it may begin after the headache phase has commenced or continue into the headache phase.

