**Figure 6. Determination of absence of moderate/severe headache by T hours (1, 2, 3, 4, 6, 8 hours) (responder)**

**Figure 7. Determination of absence of severe headache by T hours (1, 2, 3, 4, 6, 8, 24, 48 hrs) (responder)**

The absence of a headache of any intensity by each timepoint after taking double-blind study intervention will be analyzed using the same GLMM model as primary endpoint.

Similar analyses will be performed for the absence of a headache of moderate/severe intensity and absence of severe headache by timepoint. Kaplan-Meier curves for time to development of any intensity headache (or rescue medication taken), time to development of moderate/severe headache, time to development of severe headache within 48 hours will be produced by treatment and compared between treatment using the log-rank test. In addition, Kaplan-Meier curves for time to development of moderate/severe headache (or rescue medication taken) and time to development of severe headache within 48 hours (or rescue medication taken) will be produced. Hazard ratio will be estimated from cox proportional hazard model with treatment and period factors.

For each of the 5 most common individual prodrome symptoms, the absence of any intensity, absence of moderate/severe intensity, absence of severe intensity at each timepoint will be analyzed using GLMM with additional predose baseline prodrome symptom intensity category. In addition, prodrome symptoms will be summarized by descending frequency in ubrogепant group and by intensity at predose. Same GLMM model as the primary endpoint will be performed for the absence of any intensity, absence of moderate/severe intensity, absence of severe intensity nonheadache migraine symptom at each timepoint after a headache of any intensity is reported. The absence of aura at timepoint will be analyzed using GLMM model with additional predose baseline aura status. Kaplan-Meier curves for time to absence of each of the 5 most common individual prodrome symptoms will be produced by treatment and compared between treatment using the log-rank test. Kaplan-Meier curves will also be generated censoring data collected after rescue medication for migraine associated symptoms. Hazard ratio will be estimated from cox proportional hazard model with treatment and period factors.

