		Updated the secondary and additional headache endpoints derivation in Figure 4 , Figure 5 , Figure 6 , and Figure 7	Updated based on the below assumptions: 1. Missing headache at 48 hours will lead to the endpoint within 48 hours indeterminable. 2. When 24 hours recall headache is collected, the missing headache intensity at prespecified hours before 24 hours recall headache time is assumed less severe than the 24 hours recall headache intensity.
		Added the derivation of absence of moderate/severe headache in the screening period in Figure 9 and Figure 10	The derivation of absence of moderate/severe headache in the screening period is difference from those in the DB period.
		Added analysis related COVID vaccine	COVID vaccine is collected in CRF
		Re-order secondary endpoints	Protocol Amendment 2
		Additional endpoint changed from absence of aura by timepoint to absence of aura at each timepoint	Protocol Amendment 2
		3	10 May 2022
		Added predose baseline variable in the	Predose baseline effect

SAP Version History Summary			
SAP Version	Approval Date	Change	Rationale
		analysis models of absence of any intensity, moderate/severe intensity, severe intensity for the 5 most common individual prodrome symptom, and absence of aura at each timepoint	should be controlled in the analysis model

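### Aura is tested only as absent at each scheduled entry; a cumulative aura endpoint from the same diary entries would be the better comparison

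*Protocol*

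**What the plan says.** Protocol Section 3 and SAP Table 1 list an effect on aura among the additional objectives. The only endpoint for it is "Absence of aura at each timepoint" (Protocol 9.4.1.1; likewise SAP 3.3).

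The analysis is a model at each timepoint. Protocol 9.4.1.4 ends its list of outcomes for the primary-endpoint GLMM with "and absence of aura at each timepoint". SAP 8.5 states: "The absence of aura at timepoint will be analyzed using GLMM model with additional predose baseline aura status".

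On data collection, Protocol 8.1 says "The participant will record whether aura was present or absent (up to 48 hours", without saying whether the item asks about now or about the time since the last entry. Protocol 4.1 sets the diary at "prespecified timepoints (1, 2, 3, 4, 6, 8, 24, and 48 hours) and on an event-driven basis (ie, when a headache occurs", so the unscheduled entry is triggered by headache and not by aura.

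Appendix 8 of the Protocol (1.2 Migraine with aura, criterion C) includes "each individual aura symptom lasts 5–60 minutes". Note 1 there allows three times 60 minutes when three symptoms occur, and the comments say that auras of more than an hour are not rare.

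Headache, by contrast, has cumulative endpoints (within 24 and 48 hours, and by timepoint) and Kaplan-Meier analyses. No cumulative or time-to-event analysis of aura is planned.

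**The concern.** Aura can be much briefer than the gaps between entries, which are one hour up to 4 hours after dose, then two, two, 16 and 24 hours. If the item is a snapshot, an event with a short aura between two entries counts as aura absent at every timepoint. If the item looks back, the aura is recorded, but usually at only one or two of the eight entries, so each test sees only part of the events. In both cases the plan divides a modest number of auras among eight tests and never asks whether the event had any aura after dosing. At stake is an additional objective: a null aura result could reflect the endpoint rather than the drug.

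**Working it through.** **The plan's own figures.** With 240 per treatment, 64% versus 80%, two-sided 5%, power = Φ[(d − 1.96·se0)/se1], where se0 = √(2p̄(1−p̄)/n) and se1 = √((p1(1−p1)+p2(1−p2))/n). Here se0 = 0.0410 and se1 = 0.0403, so Φ[(0.16 − 0.0803)/0.0403] = 97.6%, consistent with at least 95%. Also 480/(1 − 0.07) = 516.1. Neither document states a power, rate or effect for aura.

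**Inputs from the documents.** Entry times (Protocol 4.1); aura durations (Appendix 8); two-sided 5% tests.

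**Assumptions.** Aura in 12% of placebo events and 6% of ubrogepant events; onset uniform over 0 to 6 hours after dose; 440 events per arm treated as independent; no aura at predose.

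**Snapshot item.** For an aura of D hours (D ≤ 1), the share in progress at any one of the 1, 2, 3, 4 or 6 hour entries is D/6. The share caught by at least one entry is 5D/6. For D = 2 these are 2/6 (entries from 2 to 6 hours) and 100%.

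Example, 30 minutes:
- Single entry: 0.12 × 0.0833 = 1.0% versus 0.5%, or 4.4 versus 2.2 events. Power 14%.
- Any entry: 0.12 × 0.417 = 5.0% versus 2.5%. Power 50%.

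| Aura duration | Share at one entry | Share at any entry | Power, best single timepoint | Power, cumulative |
|---|---|---|---|---|
| 5 min | 1.4% | 7% | 5% | 12% |
| 20 min | 5.6% | 28% | 10% | 35% |
| 30 min | 8.3% | 42% | 14% | 50% |
| Uniform 5–60 min | 9.0% | 45% | 14% | 53% |
| 60 min | 16.7% | 83% | 23% | 80% |
| 120 min | 33.3% | 100% | 41% | 88% |

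**Item that looks back to the last entry.** The 6 hour entry covers the most time within the onset window. It sees (2 + D)/6 of auras: 34.7% for 5 minutes and 66.7% for 120 minutes. Power there is 43% and 71%. The cumulative endpoint captures all auras, so 12% versus 6% gives 88%.

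**Sensitivity (snapshot, aura halved).**
- Aura in 25% versus 12.5% of events, uniform 5–60 minutes: 26% single against 85% cumulative. With 120 minutes: 73% against nearly 100%.
- Onset spread over 0 to 24 hours, uniform 5–60 minutes: 7% against 22% at 12% versus 6%; 9% against 41% at 25% versus 12.5%.
- 25% versus 12.5%, uniform 5–60 minutes, onset 0 to 6 hours, with 240 or 480 events per treatment instead of 440: 16% or 27% single against 60% or 88% cumulative.

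The ordering is structural. The share of auras seen at any entry cannot be smaller than the share seen at one entry, so for the same relative reduction the cumulative comparison rests on at least as many events.

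**The case against.** A reader might infer that the schedule misses most auras and that the planned tests have almost no power. The documents do not support either statement.

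- The 5 to 60 minutes applies to each symptom and is one of six characteristics, of which three are needed. Auras of 60 and 120 minutes are caught in 83% and 100% of cases above. Capture for uniform 5–60 minute auras runs from 16% to 54% as the assumed onset window changes from 0–24 to 0–4 hours.
- With a look-back item no aura between completed entries is lost, and the recall wording is not given.
- With no aura rate, effect or onset pattern in the documents, single-timepoint power depends wholly on assumptions; it ranges here from 5% to 73%.
- The expectation of no auras at 8, 24 and 48 hours, and hence of a model that cannot be estimated there, follows only from confining onset to 0–6 hours.

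These points stand and limit the claim. It is also true that the timepoint analysis has a use: with predose aura status in the model, it describes resolution of aura already present. The wording was deliberate too; the SAP version history records "Additional endpoint changed from absence of aura by timepoint to absence of aura at each timepoint".

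What the objection does not answer is the absence of any cumulative aura comparison, which does better in every scenario run, including long auras and a look-back item.

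**Conclusion.** The point holds as a low-severity improvement. For a named objective, the plan uses only single-timepoint tests where a cumulative endpoint from the same entries would be more powerful. Under the stated assumptions the gain is from about 5–41% to 12–88% for a snapshot item, and from about 43–71% to 88% for a look-back item. These figures rest on assumed aura rates, a halving of aura, uniform onset over 0–6 hours and 440 independent events per arm, so they show direction and rough size and do not forecast this trial's power. A reader should not infer that a confirmatory conclusion is at risk: aura is an additional endpoint, outside the serial gatekeeping over the primary and three secondary endpoints, and no power is claimed for it.

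**What to change.** In Protocol 9.4.1.1 and 9.4.1.4 and SAP 3.3 and 8.5:

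- Add no aura recorded within 24 hours, and within 48 hours, after dose. Derive it from all entries at which aura was recorded, restrict it to events without aura at predose, analyse it with the planned GLMM, and make it the headline aura comparison.
- Keep the results at each timepoint as descriptive.
- State the recall period of the aura item.
- Define missing status by whether the scheduled aura entries were completed. The primary endpoint's rule should not be borrowed: it rests on a 24-hour headache recall (Protocol 9.4.1.2), and no aura recall is documented.
- Describe the result as aura recorded, and acknowledge the undercount if the item is a snapshot.
- If aura is also asked at headache-triggered entries, show the result from scheduled entries alone beside it, because the arm with more headaches then has more occasions to record aura.

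The cost is one derived variable and one more model for each window, on data already collected. The cumulative endpoint does not describe aura duration, and with a snapshot item it still undercounts.

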9.4.2. Safety Analyses

The safety analysis will be performed using the safety population and will be fully defined in the SAP. The safety parameters will include AEs, clinical laboratory tests, ECGs, vital signs, and the C-SSRS. For each of the clinical laboratory tests, vital signs, and ECG parameters, the last nonmissing safety assessment before the first dose of double-blind study intervention will be used as the baseline for all analyses of that safety parameter.

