This visit will occur 4 days (-2/+4 days) after double-blind study intervention is taken for the first qualifying prodrome event. It can occur as early as 2 days after taking double-blind study intervention (after the 48 hour assessment has been completed) and as late as 8 days after taking

double-blind study intervention; however, participants should be encouraged to come in for this visit as soon as possible after completing their 48 hour assessments.

The following study procedures will be carried out at the Posttreatment Visit (Visit 3):

- Register the participant's visit in the IWRS
- Collect vital sign measurements (sitting and standing systolic and diastolic BP, sitting and standing pulse rate, respiration rate, temperature, and weight)
- Review concomitant medication
- Review and assess AEs
- Assess C-SSRS on eTablet (the *Since the Last Visit* assessment of the C-SSRS will be completed)
- Perform urine pregnancy test (for WOCBP only)
- Review eDiary entries and ensure all questions and assessments were completed. Ensure the eDiary is functioning appropriately, sending data as programmed, and the participant continues to understand how to use the eDiary. Complete retraining if needed. Redispense the eDiary back to the participant.
- Collect side effects diary. Review the side effects listed on the diary and enter identified AEs in EDC. Provide participant with new side effects diary.
- Collect study intervention blister package; review compliance against the information collected in the eDiary.
- Obtain the kit number for study intervention in IWRS and dispense a blister card with the study intervention for the second qualifying prodrome event. Review dosing instructions with the participant again if needed.

For those participants participating in the optional PK substudy:

- Collect the DBS samples that the participant collected at home and ensure that the collection dates and times are recorded in the eDiary
- Review collection timing, handling, and storage of DBS samples that will be collected at home after the second qualifying prodrome event. Provide the participant with the supplies for PK sample collection.

The first and second qualifying prodrome events must be 2 separate and distinct events that are at least 7 days apart.

Posttreatment Visit (Visit 4) After Treatment of Second Qualifying Prodrome Event/ ET Visit

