8.2.2. Vital Signs

Vital sign measurements, including sitting and standing BP, sitting and standing pulse rate, respiratory rate, temperature, body weight, and height (at Visit 1 only), will be performed at every visit.

Sitting and standing BP and pulse rate will be determined as follows: BP and pulse measurements will be performed after the participant sits quietly for 5 minutes, followed by a second set of measurements taken after the participant stands for 3 minutes (but no longer than 10 minutes).

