The second secondary endpoint, ie, ability to function normally over 24 hours after taking double-blind study intervention during the prodrome, includes the repeated measures of dichotomized FDS response at each postdose timepoint over 24 hours. The dichotomized response takes value 1 if the participant records *no disability, able to function normally* on the FDS, and takes value 0 otherwise. The repeated binary responses will be analyzed using a GEE model with a logit link. The GEE model will include period, treatment, time, treatment-by-time interaction as categorical fixed effects, predose baseline FDS score for the period, and predose baseline-by-time interaction as covariates. An unstructured working correlation matrix will be used for the repeated measures within each participant. The treatment effect will be expressed in terms of the geometric mean of the odds ratios of ubrogepant 100 mg relative to placebo estimated at the scheduled timepoints within 24 hours after taking double-blind study intervention.

A serial gatekeeping procedure will be used to control the overall type I error rate at the 0.05 level for multiple comparisons across the primary and 3 secondary efficacy endpoints. The

primary endpoint will serve as the gatekeeper for the first secondary endpoint. The first secondary endpoint will serve as the gatekeeper for the second secondary endpoint, which, in turn, serves as the gatekeeper for the third secondary endpoint.

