## **9.0 Safety Analyses**

### **9.1 General Considerations**

- Safety analyses will be performed based on the safety population.
- Safety analysis will be presented by treatment or study intervention participants actually received (placebo or ubrogepant 100 mg) unless specified otherwise.
- The baseline for safety endpoints is defined as the last non-missing assessment prior to the first dose of the double-blind study intervention.

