### **9.4 Analysis of Vital Signs**

Descriptive statistics for vital signs (systolic and diastolic blood pressures, pulse rate, respiratory rate, and temperature) at baseline, postbaseline, and changes from baseline values at each postbaseline timepoint will be presented by study intervention. An assessment will be assigned to the most recently administered study intervention. Vital sign values will be considered PCS if they meet both the observed value criterion and the change from baseline value criterion, if both criteria are available, or meet either the observed value criterion or the change from baseline value criterion that will be detailed in Table C-3.

The number and percentage of participants who have PCS postbaseline vital sign values will be calculated relative to the number of participants who have available baseline or non-PCS baseline (for parameters with only the observed value criterion) values and at least 1 postbaseline assessment. The numerator will be the total number of participants with at least 1 PCS postbaseline value during the qualifying prodrome event.

A supportive listing of participants with PCS postbaseline values will be provided.

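### A vital-sign abnormality that first appears at Visit 3 and is still present at Visit 4 is counted as potentially clinically significant under both treatments

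*Protocol*

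**What the plan says.** Both documents set one safety baseline. Protocol 9.4.2 states that "the last nonmissing safety assessment before the first dose of double-blind study intervention will be used as the baseline for all analyses" of the parameter concerned. SAP 9.1 agrees: "The baseline for safety endpoints is defined as the last non-missing assessment prior to the first dose of the double-blind study intervention". Neither defines a second safety baseline for Period 2.

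On timing, Protocol 8.2.2 lists vital signs, ending with "body weight, and height (at Visit 1 only), will be performed at every visit", so they are measured at Visits 1, 2, 3 and 4. The Visit 3 procedures in Protocol Section 8 include vital signs and also instruct the site to "dispense a blister card with the study intervention for the second qualifying prodrome event". The second dose cannot be taken before Visit 3.

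On attribution, SAP 9.4 says: "An assessment will be assigned to the most recently administered study intervention". Visit 3 therefore belongs to the first treatment and Visit 4 to the second. Protocol 9.4.2.3 is less explicit, placing the assessment under the last intervention received, but the SAP settles it.

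A vital sign is PCS if it meets both the observed-value and the change criterion where both exist, and otherwise whichever one exists (SAP 9.4, Table C-3). The numerator is participants with at least one PCS postbaseline value. No rule removes a participant who was already PCS before dose 2.

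**The concern.** A by-treatment table of PCS values is read as showing abnormalities that arose after each treatment. Under these rules, an abnormality that arose after dose 1 and did not resolve also appears against the treatment given second, although it was on record before that dose was taken. In Sequence B, a case that arose after ubrogepant is entered under placebo as well. In Sequence A the reverse happens.

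Elsewhere the plan separates the periods. Adverse events are assigned to one intervention by when they occurred (Protocol 9.4.2.1, SAP 9.2.1), and the functional-disability model adjusts for the "predose baseline FDS score for the period". Vital signs are the one change-from-baseline safety measure with a scheduled reading between the two doses, yet that reading is not used to decide whether a Visit 4 abnormality is new.

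**Working it through.** The documents give no figure for this point, so there is none to reproduce. I traced the rule for single participants and then for the two columns.

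**Single participants (Table C-3 criteria, illustrative values)**

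- Systolic pressure, PCS high if at least 180 with a rise of at least 20. Baseline 150, Visit 3 182, Visit 4 182. The rise is 32 at both visits, so the participant is PCS under the first treatment and again under the second.
- Weight, PCS high if the rise is at least 7%. Values 80, 86, 86 kg. The rise is 6/80 = 7.5% at both visits, so it is also counted twice.
- The change criterion gives little protection for sitting systolic pressure. Exclusion 5.01 bars values above 160 at Visits 1 or 2, so a later 180 is automatically a rise of at least 20 from a qualifying Visit 2 value.

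**Columns**

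Assumed quantities, none of them in the documents: s is the background rate of new PCS values per period, p is the excess caused by ubrogepant, and q_b and q_d are the chances that a background or a drug-caused PCS value at Visit 3 is still present at Visit 4. Sequences are equal, everyone takes both doses, and small overlap terms are ignored.

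- Sequence A: Period 1 placebo = s; Period 2 ubrogepant = s + p + q_b·s
- Sequence B: Period 1 ubrogepant = s + p; Period 2 placebo = s + q_b·s + q_d·p
- Ubrogepant column (mean of its two periods) = s + p + q_b·s/2
- Placebo column = s + (q_b·s + q_d·p)/2
- Difference = p(1 - q_d/2)

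Background persistence adds q_b·s/2 to both columns and cancels in the difference. Only q_d changes the difference.

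With s = 2%, p = 2% and 258 participants per sequence:

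| q_b | q_d | Ubrogepant | Placebo | Difference (points) | Participants counted twice |
|---|---|---|---|---|---|
| 0 | 0 | 4.0% | 2.0% | 2.0 | 0 |
| 0.5 | 0 | 4.5% | 2.5% | 2.0 | 258 × (0.01 + 0.01) = 5.2 |
| 1 | 0 | 5.0% | 3.0% | 2.0 | 258 × (0.02 + 0.02) = 10.3 |
| 0.5 | 0.5 | 4.5% | 3.0% | 1.5 | 258 × (0.01 + 0.02) = 7.7 |
| 1 | 1 | 5.0% | 4.0% | 1.0 | 258 × (0.02 + 0.04) = 15.5 |

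Keeping the overlap terms changes the last two rows only slightly, to 4.48% vs 2.98% and 4.96% vs 3.96%.

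**How large q_d could be**

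The treated events are at least 7 days apart and Visit 4 is at least 2 days after dose 2, so Visit 4 falls at least 7 + 2 = 9 days after dose 1. Protocol 2.1 says potentially effective concentrations last 15 hours after 100 mg. Protocol 9.4.1.2 and SAP 8.3.3 describe the washout as far longer than five half-lives. These statements make q_d likely small, though they do not show it to be zero.

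**The case against.** The strongest reply is that a common untreated baseline is a legitimate choice that both documents state consistently. That stands: the baseline itself is not an error.

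It is also fair to say that the efficacy analogy is loose. The functional-disability baseline is rated just before each treated event, whereas Visit 3 is a clinic reading 2 to 8 days after dose 1 and possibly weeks before dose 2.

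There are safeguards elsewhere. Vital-sign findings judged clinically significant become adverse events (Protocol 10.3.1) and are attributed once, a PCS listing is planned, and no hypothesis test uses these tables. This limits the consequence but does not remove the double count from the table.

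Making Visit 3 the Period 2 baseline would do harm:

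- **Mean changes.** Suppose ubrogepant shifts a vital sign by e at the next visit and the shift then washes out. With the common baseline the columns average e and 0, a difference of e. With Visit 3 as the Period 2 baseline, the placebo change in Sequence B is 0 - e, the placebo column averages -e/2, and the difference becomes 1.5e.
- **Recovered weight.** Values 80, 86.4, 80 kg would give (80 - 86.4)/86.4 = -7.4%, a false PCS low.
- **Cumulative rise.** Systolic values 150, 178, 185 are PCS at Visit 4 against the common baseline (+35), but would be missed against Visit 3 (+7).

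This objection stands in full and determines the form of the fix.

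A reader might infer that a real ubrogepant signal would be materially diluted, by close to half for weight. The documents do not support that. It would require the drug-caused part to persist to Visit 4, and for weight a lasting change of at least 7% caused by a single dose.

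**Conclusion.** The double count follows directly from the stated baseline, attribution and numerator rules, and nothing in either document prevents it. Its main effect is to raise the PCS rates in both columns: the background component becomes s(1 + q_b/2), so it is up to 50% higher if every background abnormality persists. The treatment difference shrinks only by the factor 1 - q_d/2, from nothing at q_d = 0 to 50% at q_d = 1. On the documents' own washout statements, the lower end is the more likely. All rates and persistence values here are assumptions.

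The point covers vital signs only, including weight and orthostatic changes. Laboratory tests and ECG are not scheduled at Visit 3 and are unaffected. The efficacy analyses are untouched. This is a minor improvement to descriptive safety tables.

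**What to change.** In SAP 9.4, keep the pre-first-dose baseline for mean changes and for the PCS change criteria. Add one rule: a PCS value counts under the second treatment only if the participant was not already PCS, for the same parameter and direction, at the last assessment before dose 2 (Visit 3). Restrict the Period 2 denominator in the same way, and flag persisting cases in the listing. Do not replace the baseline with Visit 3.

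The rule counts the 150, 182, 182 participant once. It still counts 150, 178, 185 under the second treatment, and it raises no flag at Visit 4 for weights of 80, 86.4, 80 kg.

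The cost is one extra derivation and a slightly smaller Period 2 denominator. At the illustrative Visit 3 rates of 4% and 2%, about 258 × (0.04 + 0.02) = 15.5 of 516 participants would leave it. No new data are needed.
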